#### **Data Storage:**

Hard copy data will be collected and stored in a password-protected computer located in the Division of PM&R. Participants will each be assigned an ID number that will be used as the sole identifier on any documents. Participant data will be compiled onto a single password protected file, where they will only be identified by their ID number. An enrollment log will be the only file where subject names are correlated with ID numbers. This will be kept in a separate, secure, password-protected file in the Division of PM&R.

#### **Data Analysis Plan**

The primary outcome will be the proportion of participants with 50% or greater reduction in neck and arm pain on the NRS pain score at the 1-month follow-up assessment. Secondary outcomes included reduction in median NRS pain score (both neck pain and arm pain), NDI-5, MQS III, opioid consumption in daily morphine equivalents, PGIC score, and satisfaction score. Secondary outcomes will also be defined based on categorical “responder analysis” definitions of important clinical change given the National Institutes of Health recommendation for responder analysis in the assessment of therapeutic spine pain interventions. The responder analysis will include the proportion of patients with 30% or greater improvement on the NDI-5, a PGIC score less than 3 (indicating “improved” or “very much improved”), a 6.8 or greater point reduction on the MQS III score (equivalent to approximately 10 daily morphine equivalents), and the proportion of participants who undergo surgical spine surgery.

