#### Inclusion Criteria:

- 1) Age 18-80.
- 2) Clinical diagnosis of unilateral C4-C8 radicular pain.
- 3) Magnetic resonance imaging pathology consistent with clinical symptoms/signs.
- 4) Numerical Rating Scale (NRS) pain score of 4 or higher.
- 5) Pain duration of more than 6 weeks despite trial of conservative therapy (medications, physical therapy, or chiropractic care).

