#### **Data Collection:**

An electronic data collection sheet (via iPad) will be used to record all pre-procedure data (see data collection sheet):

- 1) Age (years).
- 2) Sex.
- 3) Height (cm).
- 4) Weight (Kg).
- 5) Duration of pain (weeks).

- 6) Location of cervical radicular pain based on clinical diagnosis: C2, C3, C4, C5, C6.
- 7) Radiologic diagnosis based on MRI of the Cervical Spine.

Before an initial injection, the following measures will be obtained:

- 7) NRS for pain; separate scores for neck pain and for arm pain
- 8) Neck Disability Index (NDI-5)
- 9) Medication Quantification Scale (MQS III) score
- 10) Daily opioid use in morphine equivalents

Immediately after injection the following will be obtained:

- 11) Fluoroscopy time
- 12) Post-injection NRS pain score; separate scores for neck pain and for arm pain
- 13) Adverse events, if they occurred

At intervals of 2 weeks, 1 month, 3 months, 6 months, and 1 year after injection, outcome measurements will be repeated. The Patient Global Impression of Change (PGIC) and a patient satisfaction score (five-point Likert scale: 1, very dissatisfied; 2, dissatisfied; 3, neither satisfied nor dissatisfied; 4, satisfied; and 5, very satisfied) will also be recorded. A single researcher blinded to group assignment collected all follow-up assessments in person, by e-mail, by telephone, or by mailed questionnaire.

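### Participants who enter on little or no medication cannot meet the 6.8-point MQS III responder rule, which dilutes the absolute difference on one secondary outcome

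*Combined protocol and SAP*

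**What the plan says.** The Data Analysis Plan lists several secondary responder definitions. For medication use the criterion is "a 6.8 or greater point reduction on the MQS III score", a change the plan equates with roughly 10 morphine equivalents a day. The list is introduced as proportions of patients: "The responder analysis will include the proportion of patients with 30% or greater improvement on the NDI-5", followed by the other definitions. No definition limits the denominator by baseline value.

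The Inclusion Criteria admit people with "Pain duration of more than 6 weeks despite trial of conservative therapy (medications, physical therapy, or chiropractic care"). Medication is one of three alternatives, and a past trial of medication need not be continuing at entry. The only score required at entry is a "Numerical Rating Scale (NRS) pain score of 4 or higher". There is no minimum for MQS III or for opioid use.

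Under Data Collection, the "Medication Quantification Scale (MQS III) score" is recorded before the initial injection, but nothing in the plan uses it to decide who can be assessed for response. The Data Analysis Plan also names "MQS III, opioid consumption in daily morphine equivalents, PGIC score, and satisfaction score" as secondary outcomes in their own right. The Statistical analysis section assigns a t test to numerical data and a chi-square or Fisher exact test to categorical data. It mentions no baseline adjustment for these group comparisons.

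**The concern.** An absolute threshold combined with no entry minimum creates a floor. A participant who starts at 6 and stops all medication falls by 6 points and is counted as a failure. A participant who starts at 0 can only be a failure. The pain and NDI-5 responder rules are percentage reductions, and pain also has an entry minimum. The MQS III rule has neither feature.

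Medication utilization is one of the comparisons named in the Introduction, which also mentions the potential to reduce opioid use. A small difference on this outcome could be read as little effect on medication when part of the sample had no room to change. The stake is how one secondary result is interpreted and how much power it has.

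**Working it through.** **Inputs from the documents.** The threshold is an absolute fall of 6.8 points, with no baseline condition (Data Analysis Plan). The expected evaluable number is 40 per group, with 50 recruited per group and 20% attrition by 6 months (Power Analysis). The test is chi-square or Fisher exact (Statistical analysis).

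**Inputs assumed.** MQS III cannot go below 0. Alpha is two-sided 0.05; the document mentions P < 0.05 only for the lumbar studies it cites. The share f starting below 6.8 and the response rates p1 and p2 among those able to respond are not given, so a range is shown.

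**Step 1: the plan's own figure.** 40 / (1 − 0.20) = 50 per group, 100 in total, which matches the Power Analysis. The plan states no responder rate, effect size or power for any outcome, so there is no power figure to reproduce.

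**Step 2: effect of the floor.** With the same f in both arms, the all-participant rates are q1 = (1 − f)p1 and q2 = (1 − f)p2. It follows that:
- the difference is (1 − f)(p1 − p2), which shrinks by the factor (1 − f);
- the ratio is q1/q2 = p1/p2, which is unchanged.

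**Step 3: numbers.** Approximate power is Φ{[|q1 − q2| − 1.96·√(2q̄(1 − q̄)/n)] / √([q1(1 − q1) + q2(1 − q2)]/n)}, with q̄ the mean of q1 and q2. Fisher power is by exact enumeration. For the restricted analysis, n = 40(1− f) per arm and the rates are p1 and p2.

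| Assumed p1 vs p2 | f | All-participant rates | Difference (points) | Risk ratio | Power, n = 40 (Fisher) | Restricted n per arm | Restricted power (Fisher) |
|---|---|---|---|---|---|---|---|
| 50% vs 30% | 0 | 50% vs 30% | 20 | 1.67 | 45% (37%) | 40 | 45% (37%) |
| 50% vs 30% | 0.2 | 40% vs 24% | 16 | 1.67 | 33% (25%) | 32 | 37% (30%) |
| 50% vs 30% | 0.5 | 25% vs 15% | 10 | 1.67 | 20% (14%) | 20 | 25% (16%) |
| 60% vs 30% | 0 | 60% vs 30% | 30 | 2.0 | 78% (73%) | 40 | 78% (73%) |
| 60% vs 30% | 0.4 | 36% vs 18% | 18 | 2.0 | 44% (36%) | 24 | 55% (47%) |

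Worked example for 50% vs 30% at f = 0.2: q1 = 0.8 × 0.50 = 0.40, q2 = 0.8 × 0.30 = 0.24, q̄ = 0.32. The numerator is 0.16 − 1.96 × 0.1043 = −0.0444 and the denominator is 0.1028, so power is Φ(−0.43) = 33%.

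Restricting the denominator restores the 20- or 30-point difference. Power rises in each diluted case, but not to its f = 0 value, because n falls.

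**Step 4: chance imbalance in f.** With f = 0.4 and 40 per arm, the standard deviation of the between-arm difference in f is √(2 × 0.4 × 0.6/40) = 0.110. If 40% of those able to respond do so in both arms, this moves the responder difference by 0.40 × 0.110 = 0.044. The overall responder rate is then 0.6 × 0.40 = 0.24, and the standard error of the difference is √(2 × 0.24 × 0.76/40) = 0.096. The 4.4 points are one component of the 9.6-point standard error that the planned test already allows for.

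**The case against.** The strongest reply is that the all-participant proportion is a legitimate quantity. It gives the share of everyone treated who achieved an important medication reduction, which suits the Introduction's interest in opioid use and healthcare utilization. Restricting to those who start at 6.8 or more asks a different question about a subgroup. This stands, and is why the all-participant figure should be kept.

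A reader might infer that the floor biases the comparison. The documents do not support that. Treatment is randomised, so f is balanced in expectation, the floor favours neither arm, and the risk ratio is unchanged. A reader might also infer that a chance imbalance in baseline medication would pass for a treatment effect. In a single trial it can shift the estimate, but Step 4 shows that this variation is already within the test's error rate and adds no false positives.

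Three further replies have weight:
- The plan does not rely on this dichotomy alone, since MQS III itself and daily morphine equivalents are also secondary outcomes. This is partial cover, because participants at the floor dilute those means too and the planned t test does not adjust for baseline.
- The gain from restriction is modest: Fisher power goes from 25% to 30% at f = 0.2, and from 14% to 16% at f = 0.5, in the 50% vs 30% case. The cut also leaves a graded floor. A participant starting at 7 must lose 6.8/7 = 97% of the score to respond, and one starting at 20 must lose 6.8/20 = 34%.
- Percentage rules have baseline problems of their own, since a baseline of 0 at one pain site leaves a percentage reduction undefined. The contrast with the other responder definitions should not be pressed far.

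**Conclusion.** The point holds as a minor one. As written, the rule makes anyone entering below 6.8 a fixed non-responder, and eligibility permits such entry. The absolute difference is multiplied by (1 − f). Under an assumed 50% vs 30%, 20 points become 16 at f = 0.2 and 10 at f = 0.5, and approximate power with 40 per arm falls from 45% to 33% and 20%.

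The direction follows from the definition, given a scale that cannot go below 0. The size does not, because no baseline MQS III distribution is given. It would be wrong to infer that many participants will start below 6.8: the Inclusion Criteria make it possible, and the documents do not show it to be common. The effect is dilution and loss of power on one secondary responder outcome. The primary outcome, based on NRS pain at 1 month, is untouched.

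**What to change.** Make two changes in the Data Analysis Plan and the Statistical analysis section.

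1. For all participants, compare follow-up MQS III between arms with adjustment for its baseline value (for example ANCOVA), in place of the unadjusted t test. The baseline score is already collected, so this needs no new data.
2. Prespecify the 6.8-point responder proportion among participants with baseline MQS III of at least 6.8. State how many such participants there are in each arm, and report the all-participant proportion alongside. The subset is defined by a score taken before injection, so treatment cannot alter its membership.

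The cost is a few sentences of text. The downside is a smaller denominator for the restricted analysis (32 per arm at f = 0.2 and 20 at f = 0.5, if 40 per arm are evaluable). It recovers the difference but only part of the power. Fixing both denominators in advance also avoids choosing between them after the data are seen.

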Two distinct techniques used to administer epidural steroids specifically to the nerve root affected in a radicular pain syndrome, which include transforaminal access at the level of pathology and interlaminar interlaminar access at the C7-T1 level with subsequent advancement of an epidural catheter to the level of pathology. Use of an epidural catheter is necessary in order to achieve a targeted injection via an interlaminar approach in order to prevent dural puncture or direct spinal cord trauma. Anatomic studies confirm the distance between the ligamentum flavum and dura is on average, 4 mm at the C7-T1 or C6-C7 levels, but 1mm or smaller at C5-C6 and more rostral levels. Therefore, there is likely greater risk of dural puncture and spinal cord injury when “targeting” steroid delivery using only the interlaminar technique directly at the level where pathology is located (C4-C5, or C5-C6, for example). Thus, the interlaminar placement of a needle rostral to the C6-C7 level has been strongly discouraged.

Both the transforaminal injection approach and the targeted catheter approach demonstrate effectiveness. Studies have demonstrated the effectiveness of transforaminal epidural steroid injection for the treatment of cervical radicular pain. Our own recent work demonstrates the clinical effectiveness of the catheter-based targeted approach. However, these two approaches have never been directly compared. Thus, we aim to compare the differences in pain reduction, medication utilization, functional outcomes, patient satisfaction, and surgical rate reduction between these two approaches to the treatment of cervical radicular pain.

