#### Exclusion criteria:

- 1) Refusal to participate, provide consent, or provide follow-up information for the 6-month duration of the study.
- 2) Contraindications to Cervical ESI (active infection, bleeding disorders, current anticoagulant or antiplatelet medication use, allergy to medications used for CIESI, and pregnancy).
- 3) Cervical spinal cord lesions; cerebrovascular, demyelinating, or other neuro-muscular muscular disease.
- 4) Current glucocorticoid use or ESI within past 6 months.
- 5) Prior cervical spine surgery.
- 6) Patient request for or requirement of conscious sedation for the injection procedure.

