## **Power Analysis**

Size of study groups: 40; 80 total participants.

The necessary sample size was determined based on a review of past literature and power analysis. While no head-to-head studies of targeted approaches to ESI have been performed in the cervical spine, such studies have been conducted in the lumbar spine. Studies that used sample sizes of 20-30 participants per treatment group showed statistically significant differences ( $P < 0.05$ ). We will thus plan to recruit 100 participants (50 per group) in anticipation of a 20% attrition rate by 6-month follow-up, which would still result in approximately 40 participants per group, to allow for improved power to detect a difference between groups compared to the prior cited similar literature.

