#### Statistical analysis

Means and standard deviations of subject demographic data, as well as pain, functional, and treatment satisfaction scores will be calculated. Intergroup differences will be assessed by t test for numerical data and Chi Square or Fisher Exact test for categorical data. Regression modeling will be implemented using ANOVA to assess for patient traits and characteristics that increase the likelihood of efficacy using one technique as opposed to the other.

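### Surgery is analysed as a plain proportion although 20% loss by 6 months is expected, so the reported rate would depend on an unstated denominator; time to surgery with censoring would avoid this.

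*Combined protocol and SAP*

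**What the plan says.** The Introduction names surgery as one of the comparisons the trial is to make: "patient satisfaction, and surgical rate reduction between these two approaches to the treatment of cervical radicular pain". The Data Analysis Plan turns this into a secondary responder item, "the proportion of participants who undergo surgical spine surgery". It gives no time horizon, no denominator and no rule for participants whose follow-up ends early.

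Statistical analysis assigns "Chi Square or Fisher Exact test for categorical data". It mentions no time-to-event method and no handling of missing follow-up.

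The plan itself foresees incomplete follow-up. Under Power Analysis, 50 per group are recruited "in anticipation of a 20% attrition rate by 6-month follow-up", "which would still result in approximately 40 participants per group". Data Collection states: "At intervals of 2 weeks, 1 month, 3 months, 6 months, and 1 year after injection, outcome measurements will be repeated". The first exclusion criterion, however, refers to willingness to "provide follow-up information for the 6-month duration of the study". No attrition figure is given beyond 6 months.

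The numbered items under Data Collection include neither surgery nor its date.

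**The concern.** Spine surgery can occur at any point during follow-up. A participant last seen at 3 months has been observed for a quarter of the year. A single yes/no per participant cannot express that, so the analyst has to choose a denominator, and each choice treats the lost participant differently:

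- **All randomised:** surgery after last contact is counted as no surgery.
- **Known status** (surgeries seen, plus participants surgery-free at the last visit): a surgery seen in someone later lost stays in, but surgery-free participants who are lost drop out of the denominator.
- **Completers only:** surgeries already observed in people lost later are discarded, along with their surgery-free time.

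The choice could be made after the data are seen. At stake is the absolute surgical rate, which the background section links to reduced surgery and healthcare cost. If loss differs between arms, the comparison is at stake as well.

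**Working it through.** **Inputs from the documents.** 50 per group, 20% loss by 6 months, last visit at 1 year. The plan's attrition figure reproduces: 40 / (1 - 0.20) = 50 per group, and 50 × 0.80 = 40.

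**Assumptions, not in the documents.** A true 12-month surgery rate r of 10% (5% and 20% also tried), a constant surgery hazard, loss at a constant rate up to 6 months and unrelated to surgery. After 6 months loss either stops (80% still followed at 1 year) or continues at the same rate (0.80² = 64% still followed).

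**Formulas, time in years.** h = -ln(1 - r) = -ln(0.90) = 0.1054; g = -ln(1 - 0.20) / 0.5 = 0.4463; h + g = 0.5516; h/(h + g) = 0.1910.

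*Surgeries observed, as a share of all randomised:*

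- Loss stops at 6 months: 0.1910 × (1 - e^(-0.2758)) + 0.80 × (e^(-0.0527) - e^(-0.1054)) = 0.0460 + 0.0389 = 0.085.
- Loss continues: 0.1910 × (1 - e^(-0.5516)) = 0.081.

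*Known status:* observed / (observed + surgery-free completers).

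- Loss stops: 0.085 / (0.085 + 0.90 × 0.80) = 0.085 / 0.805 = 0.106.
- Loss continues: 0.081 / (0.081 + 0.90 × 0.64) = 0.081 / 0.657 = 0.123.

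*Completers only:* (0.10 × 0.80) / 0.80 = 0.10, and likewise with 0.64. There is no bias, but observed surgeries are discarded: (0.085 - 0.080) / 0.085 = 6%, or (0.081 - 0.064) / 0.081 = 21%.

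| Denominator | Loss stops at 6 months | Loss continues |
|---|---|---|
| All randomised | 8.5% | 8.1% |
| Known status | 10.6% | 12.3% |
| Completers only | 10.0% | 10.0% |
| True rate | 10.0% | 10.0% |

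With all randomised, the relative understatement is 1 - 0.085/0.10 = 15% or 1 - 0.081/0.10 = 19%. It is almost the same at true rates of 5% and 20%. In counts it is 50 × (0.10 - 0.085) = 0.75 to 50 × (0.10 - 0.081) = 0.95 surgeries per arm.

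**Sensitivity, all randomised.** At a 6-month horizon the understatement is about 10%. At 1 year, with surgery concentrated early or late (Weibull shape 0.5 or 2, true rate 20%) and loss occurring after time 0, it ranges from about 5% to 26%.

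**Between arms, all randomised.**

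- Equal 20% loss that stops at 6 months: true rates of 20% v 10% are seen as 17.0% v 8.5%. The risk ratio stays at 0.50 and the difference shrinks from 10 to 8.5 points.
- Unequal loss (illustrative): with 30% loss in the 20% arm and 10% in the 10% arm, the risk ratio becomes 0.60; with the losses reversed, 0.42.
- No true difference (10% in both arms), loss of 10% v 30%: 9.3% v 7.7% if loss stops, or 9.0% v 7.2% if it continues. This is a false gap of 1.5 to 1.8 points, against a standard error of √(2 × 0.10 × 0.90 / 50) = 6 points. The false-positive rate of an uncorrected chi-square test at 50 per arm rises from 5.1% to 5.6-5.9%; for Fisher it rises from 1.8% to 1.9-2.0%.

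**The case against.** A reader might infer that the plan counts lost participants as surgery-free and therefore understates surgery by 15-19%. The documents do not support that. They fix no denominator, and sizing the trial on about 40 remaining per group fits a completer analysis at least as well. Under that reading the rate is unbiased if loss is unrelated to surgery, and under the known-status reading it is overstated. The 15-19% is also a relative figure (1.5 to 1.9 percentage points at a true 10%). It rests on an assumed horizon, hazard and later attrition that the plan does not state.

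A reader might also infer that the treatment comparison is unsound. With equal loss the risk ratio hardly moves. Even with markedly unequal loss the false gap is small beside its standard error. No differential loss is predicted in the documents.

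Nor do the documents say that surgery can be learned only from the participant. They do not say how it is ascertained, and participants are patients of the treating centre.

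Finally, about 10 surgeries in total (100 × 0.10) is few for an asymptotic log-rank test, and a stated horizon and denominator with sensitivity analyses would also close the gap.

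These points limit the size and direction of the problem, and the fix takes account of the small number of events. They do not remove the problem. The stated method cannot use partial follow-up, and two of its three possible denominators are biased even when loss is unrelated to surgery.

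**Conclusion.** The concern holds as a modest one about the method for a secondary outcome. For a true 12-month rate of 10%, the reported rate could lie anywhere from about 8.1% to 12.3%, depending on a denominator the plan does not name and on loss after 6 months. This assumes a constant surgery hazard and loss unrelated to surgery. The direction of any bias cannot be read from the documents. Censoring at last known status would recover the 10% under the same assumptions and use every observed surgery. The comparison between arms is at risk mainly if loss differs by arm.

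**What to change.** Replace the surgery item in the Data Analysis Plan with:

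> Time from randomisation to first spine surgery will be estimated by Kaplan-Meier, censoring at the last contact at which surgery status was known. The 12-month cumulative incidence per arm and its difference will be reported with 95% CI, and arms compared by a log-rank test (permutation version, given few events).

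Apply this in place of the chi-square or Fisher test for this outcome only. Under Data Collection, add surgery (yes/no), its date and the date of last contact at each follow-up. Reconcile the 6-month duration in the exclusion criteria with the 1-year visit, so that the 12-month horizon has a clear basis.

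**Cost.** Short analysis text and extra data items that are not now listed: surgery status with its date, and the last-contact date. The interval will be slightly wider. The estimate assumes that loss is unrelated to surgery; the simple proportions give no protection if that fails. The permutation test is exact only if loss follows a similar pattern in both arms, so loss should be reported by arm.
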